3.4 Subject selection

3.4.1 Inclusion criteria

Subjects with solid tumors or lymphoma undergoing F-18 FDG PET/CT scan who have at least one measurable target lesion and sustain a moderate or greater infiltration.

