3.4.2 Exclusion criteria

- Subjects unwilling or unable to tolerate a repeat PET/CT scan.
- Subjects with meaningful medical intervention between PET/CT scans that would likely impact SUV.
- Subjects with follow-up moderate or greater infiltrations as determined by the PI and Lara score.
- Patients for whom an infiltration score cannot be determined, such as when ports or other central lines are used.

- Pregnant women.
- Subjects who are not able to read/understand English

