3.6.4 Data Analysis

Upon the determination of an infiltrated subject, the technical staff will notify the Nuclear Medicine physician to determine the severity and appropriateness of the subject for the study. To qualify for the study, the subject will need:

- at least one target lesion; and

- at least a moderate infiltration as determined by visual analysis and/or infiltration score from the Lucerno Dynamics' Lara™ system software

Data will be analyzed on each individual subject after the second imaging session. The scans will be presented in tandem such that simultaneous measurements may be performed using a qualified image analysis program, such as MIM version 6.5. Up to five target lesions will be assessed, chosen to include the target lesion or lesions defined under the PERCIST criteria [8]. For each lesion, SUV peak will be measured, and a volume contour will be created using mean liver SUV+2SD as a threshold., SUVmean, metabolic tumor volume, and total lesion glycolysis will be measured from the contour. The lesions chosen will be the same for each scan, however differences in the scans may affect the volume contour. Liver and blood pool measurements will also be made as for PERCIST criteria.

SUV will be descriptively compared for the original and re-test. Our expectation is that SUV will increase at the re-test, although we are not amply powered to conduct a rigorous statistical test. We will also evaluate the relationship between SUV values and the Lara score by computing a Pearson's correlation coefficient. We hypothesize this correlation will be positive.

We hypothesize that presence of venous stasis (a cessation or impairment of venous flow) may have an influence on the relationship on SUV scores. We will conduct a sensitivity analysis by conducting analyses with and without stasis cases. Specifically, we will compare the % change in SUV values between test and re-test and the correlation coefficient of % SUV change and Lara score in the samples including and excluding stasis cases.

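### Section 3.6.4 summarises severity only by Pearson's r, which gives no SUV loss per unit of Lara score and can shift when stasis cases are dropped merely because the score range changes

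*Combined protocol and SAP*

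**What the plan says.** Under 3.6.4 Data Analysis, SUV is compared descriptively between the two scans. The plan will then "evaluate the relationship between SUV values and the Lara score by computing a Pearson's correlation coefficient", with a direction-only expectation: "We hypothesize this correlation will be positive". The stasis sensitivity analysis compares two things with and without stasis cases: the percentage change in SUV, and "the correlation coefficient of % SUV change and Lara score in the samples including and excluding stasis cases". No regression, slope, interval, scatter plot or report of the score distribution is planned.

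Entry (3.4.1) is limited to patients who "have at least one measurable target lesion and sustain a moderate or greater infiltration". Section 3.6.4 says how this is judged: "at least a moderate infiltration as determined by visual analysis and/or infiltration score from the" Lara software. Section 3.4.2 excludes "Subjects with follow-up moderate or greater infiltrations as determined by the PI and Lara score". Enrolment stops at 20 patients or 12 months (3.6.3). The synopsis calls the analyses descriptive, and 3.6.4 disclaims power for a rigorous test.

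**The concern.** The study sets out to measure the impact of infiltration on SUV, and impact is a quantity. A correlation has no units. A low r could mean that SUV hardly depends on the Lara score, that the patients who came back had similar scores, or that test-retest noise was large. The planned output does not separate these.

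The stasis comparison is the more exposed use. If stasis cases cluster at one end of the score range, removing them narrows the range and changes r even when stasis does nothing to SUV. A reader could take that shift for a stasis effect. The documents do not say where stasis cases fall, so this risk is conditional.

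**Working it through.** The plan gives no figure for this analysis, so there is nothing to reproduce. It gives no Lara units, score SD, moderate threshold, residual SD or expected r. Everything below rests on assumed values, except the cap of 20 and the cited repeatability limits of −30% and +40% (section 1.0).

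**1. What r contains.** With slope b, score SD sx and residual SD se, r = b·sx / √(b²·sx² + se²).

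- *Same slope, different r.* Assume b = 5 percentage points of SUV per Lara unit and se = 15. For sx = 1, r = 5/√(25 + 225) = 0.32. For sx = 2, r = 10/√(100 + 225) = 0.55. For sx = 4, r = 20/√(400 + 225) = 0.80.
- *Same r, different slope.* Take sx = 2 and (b, se) = (2, 6), (5, 15) or (8, 24). Then r = 4/√52 = 10/√325 = 16/√832 = 0.555 each time.

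**2. Using the cited repeatability limits.** Read as 95% limits on the log scale, they give an SD of (ln 1.4 − ln 0.7)/(2 × 1.96) = 0.693/3.92 = 0.177. Assume a 0–1 score, a linear slope of 1.0 in log SUV, and uniform scores with sx = width/√12:

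| Score range | sx | r |
|---|---|---|
| 0–0.6 | 0.173 | 0.70 |
| 0.1–0.6 | 0.144 | 0.63 |
| 0.2–0.6 | 0.115 | 0.55 |
| 0.2–0.4 | 0.058 | 0.31 |

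**3. Dropping stasis cases.** In the same model, take 20 patients over 0.2–0.6 with no stasis effect and remove the four highest scores. Mean r falls from 0.54 to 0.46, and the mean slope stays at about 1.00. The r shift of −0.08 is smaller than its between-trial SD of 0.14.

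**4. How much the entry cut matters.** Start from r = 0.70 and keep the top quarter of scores. Simulated r becomes 0.44 for normal severity and 0.24 for uniform severity, and stays at 0.70 for exponential severity. The loss can be nil.

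**5. Whether a slope is stable.** This depends on the outcome scale. Suppose the score is the fraction of SUV lost. Across the four ranges in step 2, in table order, the slopes are:

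- log change: 1.48, 1.59, 1.71, 1.43
- change relative to the infiltrated scan: 2.33, 2.64, 3.03, 2.10
- change relative to the re-test: 1.01–1.02 throughout

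When the exercise in step 3 is repeated with change relative to the infiltrated scan, the mean slope itself moves from 3.02 to 2.59, a false stasis signal.

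**6. Selection by eye.** In a model with a true slope of 0.60, admit the top quarter on either Lara score or visual grade. If visual grade is unrelated to the residual, the slope stays at 0.60. If it correlates with the residual (assumed 0.4), the slope falls to 0.31.

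**7. Precision at n = 20.** By Fisher's z, r = 0.40 has a 95% CI of tanh(0.424 ± 1.96/√17) = −0.05 to 0.72. The half-width for the slope in step 1 is 2.101 × 15/(sx·√19) = 7.2, 3.6 and 1.8 for sx = 1, 2 and 4, against a slope of 5.

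**The case against.** The best defence is that this is a descriptive side analysis. The listed objectives ask for the impact of moderate or greater infiltration, which the test/re-test comparison addresses. Loss per Lara unit is not among them. The entry restriction matches the target population, no power is claimed, and the hypothesis concerns only the sign, which r and the slope share. All of that stands and limits the weight of the point. It does not make a bare r informative: a descriptive study still needs a measure in usable units with an interval.

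A second objection is that a slope is no cure. This also stands in part. The slope is stable only if the relation is near linear on the chosen outcome scale, entry by eye can bias it, and it is imprecise in a small sample. Even in the linear model of step 3, the change in slope after dropping four patients has an SD of 0.37 on a slope of 1.00.

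A reader might go further and infer that r shows only which severities returned, or that a slope could be carried unchanged to any other infiltration population. The documents support neither. r also carries slope and noise. Entry is not a clean cut on Lara score. The outcome scale that portability depends on is not fixed.

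**Conclusion.** The point holds in a limited form. The planned statistic cannot say how much SUV is lost per unit of Lara score, and the stasis contrast can show a shift in r that comes only from a changed score range, if stasis cases sit at one end of it. The size cannot be derived from the documents. Under the assumed models the effect runs from nil (entry cut with exponential severity) through a fall of 0.08 in r (dropping four of 20) to r between 0.31 and 0.70 for one underlying relation.

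The conclusion assumes that the correlation uses one value per infiltrated scan. The phrase about SUV values is ambiguous, but the stasis paragraph's use of percentage change and the positive sign expected both favour that reading. If both scans were pooled, the scores would extend below moderate.

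Because the analysis is supplementary and unpowered, this is a change to consider rather than a defect that threatens the primary result.

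**What to change.** In 3.6.4:

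- Define one outcome per patient, (re-test SUV − infiltrated-scan SUV) / re-test SUV, and name the SUV measure and lesion or lesions it uses.
- Regress it on the infiltrated-scan Lara score. Report the slope with its 95% CI, a scatter plot and the distribution of Lara scores. Keep Pearson's r as a supplement, with Spearman's if scores are skewed.
- In the stasis paragraph, compare slopes with their CIs with and without stasis cases, and show the score range of each set.
- Check linearity on the plot and limit conclusions to moderate or greater infiltrations. Do not describe the slope as free of selection bias or as precise.

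The cost is a few sentences and a few lines of code, with no new data. The downside is that the slope carries Lara units and will have a wide interval, especially if the returning patients span a narrow range of scores.

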DURATION OF SUBJECT PARTICIPATION AND DURATION OF STUDY	Patients who experience a moderate or greater infiltration will be invited for a repeat PET/CT scan. Subject participation in this study is limited only to the few minutes they are questioned after their first scan and before their repeat scan, and for the time it will take for the repeat scan. These questions are designed to try and ensure both scans were conducted under similar subject conditions (fasting levels, prior activity levels, etc.) The questions should not require more than 15 minutes total. Final data analysis will be completed within 3 months of enrolment of the final subject.
STATISTICS Primary Analysis Plan	Analyses will be descriptive in nature because the sample size of the group who will return for re-testing is challenging to forecast a priori. We anticipate enrolling up to 20 patients in 12 months based on the infiltration rate at WFB and accounting for ongoing quality improvement efforts.
Rationale for Number of Subjects	All subjects undergoing PET/CT who experience a moderate or greater infiltration will be invited back for a repeat scan.

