3.6.3 Sample size determination

The sample size of the group who will return for re-testing is challenging to forecast a priori due to ongoing quality improvement efforts to reduce infiltrations. The study will enroll patients for up to 12 months, or will be terminated at 20 patients if reached in less than 12 months.

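### The with/without comparison in 3.6.4 understates a mean stasis effect by the unstated stasis share and can mislead for the correlation with Lara score; add a direct stasis versus non-stasis summary

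*Combined protocol and SAP*

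**What the plan says.** The stasis analysis is set out in the last paragraph of section 3.6.4 that deals with SUV. It opens with a hypothesis: "We hypothesize that presence of venous stasis (a cessation or impairment of venous flow) may have an influence on the relationship on SUV scores". The analysis follows directly: "We will conduct a sensitivity analysis by conducting analyses with and without stasis cases". Two quantities are named: "we will compare the % change in SUV values between test and re-test and the correlation coefficient of % SUV change and Lara score", each obtained "in the samples including and excluding stasis cases".

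The documents plan no summary of stasis patients alone, no stasis versus non-stasis contrast and no interaction. They give no expected number or share of stasis cases.

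The setting is small and descriptive. Enrollment runs for up to 12 months or, under 3.6.3, "will be terminated at 20 patients if reached in less than 12 months". The synopsis says "Analyses will be descriptive in nature because the sample size of the group who will return for re-testing is challenging to forecast a priori", and 3.6.4 says of the main SUV comparison that "we are not amply powered to conduct a rigorous statistical test". Stasis is not among the primary or exploratory objectives in 3.6.1 and 3.6.2.

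**The concern.** The two sets being compared are nested: the set without stasis cases is the full set with those patients taken out. A comparison of nested sets shows how far the overall result depends on the stasis cases. It does not show, on its natural scale, how stasis patients differ from the others, and that is one plain reading of the hypothesis.

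The practical risk is one of interpretation. In a descriptive study the displayed number is the result. If the mean SUV change hardly moves when a few stasis patients are removed, a reader may take it that stasis has little effect, when the small movement may only reflect how few stasis patients there were. For the correlation the risk differs, because the movement need not even have the sign of the true difference between the groups.

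**Working it through.** **Inputs.** From the documents: at most 20 patients (3.6.3), the two quantities compared and the two nested sets (3.6.4). The documents state no power, effect size, SD or stasis share, so there is no figure of the plan's own to reproduce. Assumed here: the number of stasis cases s, one value per patient, means as the summary, and equal SD within groups.

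**Step 1. Mean percent SUV change.** Let N be the number of patients and p = s/N. The overall mean is p × mean(stasis) + (1 − p) × mean(non-stasis). Subtracting mean(non-stasis) gives

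mean(all) − mean(non-stasis) = p × [mean(stasis) − mean(non-stasis)].

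Illustration with assumed values: non-stasis patients rise by 20 percentage points on average, stasis patients by 40, and 4 of 20 have stasis. The overall mean is 0.2 × 40 + 0.8 × 20 = 24. The with/without difference is 24 − 20 = 4, against a group difference of 20, so one fifth is shown. At N = 20:

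| Stasis cases (assumed) | 1 | 2 | 4 | 6 | 8 | 10 |
|---|---|---|---|---|---|---|
| Share of the difference shown | 5% | 10% | 20% | 30% | 40% | 50% |

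A numerical check at N = 10 and N = 20 gave exactly these ratios. If lesions rather than patients were averaged, p would be the share of lesions.

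**Step 2. Is information lost for the mean?** In SD units, SE(with/without) = √[1/(N − s) − 1/N] and SE(direct) = √[1/s + 1/(N − s)]. For s = 4, N = 20:

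- with/without: √(1/16 − 1/20) = 0.112 SD;
- direct: √(1/4 + 1/16) = 0.559 SD.

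The ratio is 0.2 = p. Estimate and SE shrink together, so dividing by p recovers the direct contrast in full. For the mean, the fault is the scale of the display.

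**Step 3. Correlation with Lara score.** Take unit variance within each group, correlations r_n (non-stasis) and r_s (stasis), and stasis-group mean shifts dx (Lara score) and dy (percent change) in SD units. The correlation in the full sample is

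r_all = [(1 − p) r_n + p r_s + p(1 − p) dx dy] / √{[1 + p(1 − p) dx²][1 + p(1 − p) dy²]}.

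With r_n = 0.6, r_s = 0 and p = 0.2 (all assumed), the true difference is −0.60:

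- No mean shifts: r_all = 0.8 × 0.6 = 0.48. The shift is −0.12, or 20% of the difference.
- Opposite 2 SD shifts: r_all = (0.48 − 0.64)/1.64 = −0.10. The shift is −0.70, or 116%.
- Same-direction 2 SD shifts: r_all = (0.48 + 0.64)/1.64 = 0.68. The shift is +0.08, which is small and of the wrong sign (−14%).

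Over p = 0.1, 0.2 and 0.3, the opposite shifts give 78%, 116% and 138% of the true difference, and the same-direction shifts give −10% to −14%. If both groups have r = 0.6 and the shifts are opposite, r still moves by −0.42 to −0.73 although the within-group relationship does not differ. The two planned coefficients alone do not allow these cases to be told apart.

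**Step 4. What a direct contrast would offer at N = 20.** The half-width is 1.96 × SE; power is for a 1 SD difference at two-sided 0.05, normal approximation.

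| Stasis vs non-stasis (assumed) | SE (SD units) | 95% half-width | Power, 1 SD |
|---|---|---|---|
| 2 vs 18 | 0.745 | 1.46 | 27% |
| 4 vs 16 | 0.559 | 1.10 | 43% |
| 6 vs 14 | 0.488 | 0.96 | 54% |

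An interval based on the t distribution would be somewhat wider. A stasis-only correlation is barely estimable: the Fisher-z SE, 1/√(n − 3), is undefined for n of 3 or fewer, 1.0 for n = 4 and 0.58 for n = 6. That favors a plot over another coefficient.

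**The case against.** The plan calls this a sensitivity analysis, and with/without is a legitimate one. The hypothesis is loosely worded. It can fairly be read as saying that stasis cases may distort the overall SUV change and the Lara correlation, and with/without addresses that question directly. The plan sets no test, threshold or decision rule for stasis, stasis is not an objective, and every analysis is declared descriptive. For the mean, anyone who knows the number of stasis cases can divide by the share. The direct contrast would also be imprecise: even 6 cases among 20 give a half-width near 1 SD.

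Most of this stands, and it limits the point. A reader might infer that the planned analysis cannot answer its own hypothesis. That goes too far, because Step 2 shows that nothing is lost for the mean. A reader might also infer that only 10% to 30% of any stasis effect will be seen. Those figures require 2 to 6 cases among 20, which the documents do not state, and Step 3 shows that no such rule holds for the correlation in general. Nor do the documents commit the study to concluding that stasis does not matter; a misreading is possible, not planned.

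What the objection does not remove is this: the plan provides neither the rescaling nor a report of stasis counts, rescaling does not work for the correlation, and the reading of the hypothesis as a difference between stasis and other patients is left without a display on its own scale. Imprecision argues for showing the interval, not for omitting the contrast.

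**Conclusion.** The point holds as a minor one. For mean percent SUV change, the planned comparison shows the stasis versus non-stasis difference multiplied by the stasis share: 5%, 20% or 50% of it for 1, 4 or 10 cases among 20. For the correlation with Lara score, the with/without shift has no fixed relation to the true difference and can exceed it or reverse its sign, so a small shift is not evidence that stasis has no effect.

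The first result is exact for means with one value per patient; the case counts are assumed. The second rests on illustrative correlations of 0.6 and 0 and group shifts of up to 2 SD, chosen to show what can happen and not what is expected. Neither result makes the with/without analysis wrong for checking robustness.

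**What to change.** In 3.6.4, keep the with/without results and label them a robustness check of the overall estimate. Add:

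- the number of stasis and non-stasis patients, with SUV change summarized separately for each;
- the direct difference between them in per-patient SUV change, for example in mean log(re-test SUV / initial SUV), with a 95% CI, presented as descriptive; state how up to five lesions are reduced to one value per patient;
- a plot of SUV change against Lara score with stasis cases marked, in place of a stasis-only coefficient.

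State also that stasis is classified before re-test SUVs are measured, and by what rule. Section 3.6.4 gives only a short parenthetical description of stasis. The case report form and imaging charter are not reproduced in the text reviewed and may say more. Section 1.0 describes the Lara time-activity curves as showing tracer held near the injection site, not as separating stasis from infiltration, so the documents do not support assuming that the curves supply the rule.

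The cost is a few lines of text. No extra scans or patients are needed, and stasis status is already required for the planned analysis.

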2.1 Objectives of the study

2.1.1 Primary Objective

To characterize impact of moderate or greater infiltrations on standardized uptake values of solid tumors or lymphoma.

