2.1.2 Exploratory Objectives

- To estimate the impact that infiltrations may have on initial assessment and/or response assessment in accordance with PERCIST criteria.
- To estimate the effect of moderate or greater infiltrations on metabolic tumor volume and total lesion glycolysis.

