To assess the exploratory objective of whether extravasation of radiotracer could influence initial staging, for patients where the type of primary solid tumor is known the T, N, and M stages will be assessed to the extent possible by PET/CT for each scan and an overall stage assigned. This will be done even if the scan was performed for response assessment or follow up. No additional imaging or clinical information will be used and it is recognized that this assessment may not generate the true clinical stage. However, the comparison between the two scans will still provide information regarding the risk of changing stage based on missed or mischaracterized lesions after an extravasation event. To provide more granular information, the number of FDG avid regional nodes and number of FDG avid non-nodal metastases (capped at 25 each) will also be recorded for each scan.

For the exploratory objective of whether extravasation can influence apparent response to therapy, we will use the infiltrated and repeat scans to explore the impact of infiltrations on PERCIST criteria if there is an existing PET/CT scan for

comparison. This other PET/CT scan could either be a prior or a follow-on PET/CT scan that has a Lara-validated injection.

All scans will be analyzed by a qualified Nuclear Medicine physician and reported using the study imaging charter. Any measurements made for the clinical reports will not be used for this analysis. To mitigate bias, a second blinded radiologist will independently analyze the scans.

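### The two lesion counts per scan in section 3.6.4 leave out non-regional lymph nodes, so a distant node missed on the infiltrated scan can go unrecorded when stage does not change

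*Combined protocol and SAP*

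**What the plan says.** Section 2.1.2 sets the exploratory objective: "To estimate the impact that infiltrations may have on initial assessment and/or response assessment in accordance with PERCIST criteria". Section 3.6.4 carries out the initial-assessment part in two steps.

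- **Stage.** On each scan, "for patients where the type of primary solid tumor is known the T, N, and M stages will be assessed" as far as PET/CT allows, and an overall stage is assigned. This is done even when the scan was ordered for response assessment or follow-up. The comparison is meant to inform on "the risk of changing stage based on missed or mischaracterized lesions after an extravasation event".
- **Counts.** For finer detail, each scan also yields "the number of FDG avid regional nodes and number of FDG avid non-nodal metastases (capped at 25 each"). No other lesion count is given.

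Eligibility is wider than solid tumors. Section 3.4.1 admits "Subjects with solid tumors or lymphoma undergoing F-18 FDG PET/CT scan", and the primary objective in section 2.1.1 names both disease groups.

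**The concern.** The counts are there to show lesion loss that a stage category is too coarse to show. They matter most in patients whose stage cannot move much, such as those who already have metastatic disease. Because section 3.6.4 includes scans done for response assessment or follow-up, patients of this kind can be in the comparison.

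The two categories do not cover all nodal disease. One is limited to regional nodes and the other excludes nodes altogether. Nodes outside the regional basin therefore have no place to be recorded. Section 2.0 gives poor visibility of metastatic lesions on infiltrated scans as part of the motivation for the study, and a distant nodal deposit is one such lesion. At stake is whether the exploratory result on missed lesions is complete for this site.

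A smaller matter concerns scope. The text does not say whether the counts are taken only in solid-tumor patients. In lymphoma there is no solid primary to which the word regional could refer.

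**Working it through.** The plan states no figure to reproduce, so the check is one of coverage.

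**Inputs.** The count categories, the stage rule and its solid-tumor condition come from section 3.6.4. Eligible diseases come from section 3.4.1 and the cap of 20 patients from section 3.6.3. One assumption is needed: that non-regional nodal disease is scored under M. If some of it were not, the gap would be wider.

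**Step 1: coverage by lesion site (solid tumor of known type).**

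| Site of FDG-avid lesion | Regional-node count | Non-nodal count | Stage |
|---|---|---|---|
| Regional node | yes | no | N |
| Non-nodal metastasis | no | yes | M |
| Non-regional node | no | no | M only |

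The third row has no count. Its only route into the comparison is a change in M or overall stage.

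**Step 2: when that route works.** If the only metastatic disease is one distant node and the infiltrated scan misses it, the patient is M0 on that scan and M1 on the repeat. The stage comparison records the difference. If other metastatic disease is visible on both scans, the patient is M1 both times and the missed node need not alter M or overall stage.

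**Step 3: a constructed case of the second kind.** The lesion numbers are invented for illustration.

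| | Regional nodes | Non-regional nodes | Liver lesions | Total |
|---|---|---|---|---|
| Repeat scan | 2 | 4 | 1 | 2 + 4 + 1 = 7 |
| Infiltrated scan | 2 | 1 | 1 | 2 + 1 + 1 = 4 |
| Difference | 0 | 3 | 0 | 7 − 4 = 3 |

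The plan's two counts read 2 and 1 on both scans, so the recorded change is 0 and 0. M is positive on both. Three of seven lesions are missed and nothing is recorded. With a third count the same reading gives 4 against 1, a change of 3.

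**Step 4: coverage by disease.** A solid tumor of known type receives T, N, M and an overall stage. Lymphoma receives no stage, because the stage rule is conditional on a known solid primary. The documents give no split by disease. If 10% to 30% of 20 patients had lymphoma (an assumption), 0.10 × 20 = 2 to 0.30 × 20 = 6 patients would lie outside the stage comparison.

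**The case against.** The case for leaving the plan alone has four parts.

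- **Distant nodes are not lost altogether.** They enter through M, and the counts only supplement the stage comparison. This stands, and it narrows the gap to cases where M and overall stage do not move. The documents do not say how common those are.
- **The example is built to give zero.** This also stands. Had the infiltration hidden a regional node or the liver lesion, the existing counts would have shown it. The example proves that a zero is possible, not that it is frequent.
- **The imaging charter and the CRF may define further categories.** Section 3.6.4 refers to the charter, which is not among the documents, and only the heading of Appendix I is available. The charter or form may already hold a third field. The protocol sentence would then still need to match it.
- **The restriction to solid tumors is deliberate.** The condition on a known solid primary is stated openly, and the objective refers to PERCIST, which reference 8 describes as response criteria for solid tumors. This stands.

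The last part also answers a stronger reading. A reader might infer that lymphoma patients are scored as having no stage change, that the comparison is thereby biased towards no impact, and that a lymphoma stage with nodal-region and extranodal counts must be added. The documents do not support this. A lymphoma patient is assigned no stage, which places that patient outside the comparison and does not enter a zero into it. Leaving out a disease group narrows what the comparison covers; it does not by itself shift the result. Lymphoma patients remain eligible for the SUV, metabolic tumor volume and total lesion glycolysis analyses. A lymphoma staging system would be a new endpoint, not a correction.

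**Conclusion.** The point holds for solid tumors and for the counts. As written, they have no category for FDG-avid non-regional nodes, so the loss of such a node on the infiltrated scan is recorded only if it alters M or overall stage. In a patient who is M1 on both scans, the counts understate missed lesions at that site. The size in this trial cannot be estimated, since the documents give neither the frequency of distant nodal disease nor the share of patients already M1.

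For lymphoma, only a statement of scope is missing. Without one, a conclusion about staging could be extended to enrolled patients who were never part of the comparison.

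The matter is minor. It concerns a supplementary measure within one exploratory objective of a descriptive study, and no test or sample size depends on it. It rests on the protocol sentence as it stands, and on the charter and CRF not already supplying the missing category. It is worth correcting because the correction is cheap.

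**What to change.** In section 3.6.4, record three counts on each scan in place of two: FDG-avid regional nodes, FDG-avid non-regional nodes, and FDG-avid non-nodal metastases, each capped at 25. Add one sentence saying that the stage and regional-node comparison covers patients with solid tumors only and that its conclusion does not extend to the enrolled lymphoma patients. Bring the imaging charter and the CRF into line with this text.

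The cost is one or two sentences, one CRF field and a few minutes more reading per scan, with the same scans and readers. The change is best made before reading starts, because adding the count later would mean re-reading scans, possibly by readers who already know the results.
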